Phase I Dose Escalation of Monthly Intravenous Ra-223 dichloride in Osteosarcoma

Test drug(s): Ra-223 dichloride (BAY 88-8223)

Study purpose: Proof of concept of targeted Ra-223-dichloride therapy for osteosarcoma, a bone-forming cancer

Clinical study phase: I/II

Version no.: 6 Date: 13-Oct-2014

Amendment no.: 6 Date: 13-Oct-2014

Bayer Study no.: **ONC-2012-66**

Institution Study no.: **Primary Investigator:** [name] MD. Investigational Cancer Therapeutics [name]; [contact]; [contact]

[name] MD. Nuclear Medicine [name] [contact]
[contact]

Research Coordinator: [name]

Data Manager: [name], Research Data Coordinator, Investigational Cancer Therapeutics [contact]; [contact]; [contact]

Statistician: [name]

The study will be conducted in compliance with the protocol, ICH-GCP and any applicable regulatory requirements.

Confidential

The information provided in this document is strictly confidential and is intended solely for the guidance of the clinical investigation. Reproduction or disclosure of this document - whether in part or in full - to parties not associated with the clinical investigation, or its use for any other purpose, without the prior written consent of the Principal Investigator is not permitted.

Throughout this document, symbols indicating proprietary names (®, TM) are not displayed. Hence, the appearance of product names without these symbols does not imply that these names are not protected.

Synopsis

Title	Phase I Dose Escalation of Monthly Intravenous Ra-223 dichloride in Osteosarcoma
Clinical study phase	Phase I/II
Study objective(s)	
Primary objective: Determine maximum tolerated or recommended dose of monthly 223-radium dichloride in patients with recurrent or metastatic osteosarcoma. Comparison of safety and toxicity of 50, 75, and 100 kBq 223-radium dichloride /kg will be made.
 
Secondary Objective: compare alkaline phosphatase reduction to quantitative imaging techniques (^{99m}Tc-MDP, ¹⁸FDG-PET-CT, ¹⁸FNa PET-CT scans to determine objective response of osteosarcoma indicator lesions to 223-radium dichloride

Name of active ingredient	Ra-223 dichloride
Dose(s)	50, 75 or 100 kBq/kg body weight
Route of administration	Intravenous
Indication	Osteosarcoma recurrence or metastatic (bone-forming tumors)
Diagnosis and main criteria for inclusion	Osteosarcoma with 1) metastatic or recurrent disease and 2) indicator lesion(s) avid on ^{99m} Tc-MDP bone scan.
Study design	The study design is a 3+3 Phase I dose escalation (N=3/cohort) with expansion at highest safe dose (N=6); if 75kBq is 2/3 DLT, the dose -1 (50kBq/kg) is the MTD
Type of control	Uncontrolled study (i.e. no placebo or control group)
Number of subjects	Dose escalation N=14; dose expansion N=6 ;total= 20
Plan for statistical analysis	
Primary objective: Determine maximum tolerated or recommended dose of monthly 223-radium dichloride in patients with recurrent or metastatic osteosarcoma. Comparison of safety and toxicity of 50, 75, and 100 kBq 223-radium dichloride /kg will be made.
 
Secondary Objectives: Analysis change in objective measurements of alkaline phosphatase pre , before dose 4 (mid study) and at end of study (after dose 6) vs change in SUV of for PET- scans (¹⁸FDG and /or ¹⁸FNa) and of SPECT CT for ^{99m}Tc-MDP. Changes in uptake will be analyzed for dose response effects (between groups) and pre vs mid study and end of study (within group)

List of abbreviations

AE	Adverse Event
ALP	Alkaline Phosphatase
ALSYMPCA	Alpharadin in Symptomatic Prostate Cancer
ALT	Alanine Aminotransferase
ANC	Absolute Neutrophil Count
AST	Aspartate Aminotransferase
BPI-SF	Brief Pain Index (Short Form)
BSoC	Best Standard of Care
CBC	Complete Blood Count
CRO	Clinical Research Organization
CRPC	Castration Resistant Prostate Cancer
CT	Computed tomography
CTCAE	Common Terminology Criteria for Adverse Events; version 4.03
DK	Decay Correction Factor
EBRT	External Beam Radiation Therapy
ECOG	Eastern Co-operative Oncology Group
eCRF	Electronic Case Report Form
EU	European Union
GCP	Good Clinical Practice
GCL	Global Clinical Leader
GMP	Good Manufacturing Practice
HRPC	Hormone Resistant Prostate Cancer
IB	Investigator Brochure
ICF	Informed Consent Form
ICH	International Conference on Harmonization
IDMC	Independent data monitoring committee
IEC	Independent Ethics Committee
IRB	Institutional Review Board
IV	Intravenous
IxRS	Interactive Voice/Web Response System (IVR/IVRS)
kBq	KiloBecquerel; SI Unit of Radioactivity
kg	Kilogram
LHRH	Luteinizing-Hormone-Releasing Hormone; also known as Gonadotropin-Releaseing Hormone (GnRH)
mCi	Millicuries
MedDRA	Medical Dictionary for Regulatory Activities
mL	Milliliter
MRI	Magnetic Resonance Imaging
NCI	National Cancer Institute
NYHA	New York Heart Association
OS	Overall Survival
PS	Performance Status
PSA	Prostate Specific Antigen
QoL	Quality of life
SAE	Serious adverse event
SAP	Statistical Analysis Plan
SAS	Statistical Analysis Software
SRE	Skeletal-related Events
SUSAR	Suspected Unexpected Serious Adverse Reaction
TEAE	Treatment-emergent Adverse Event
ULN	Upper Limit of Normal
WHO-DD	World Health Organization – Drug Dictionary

Definitions of terms

Ra-223 dichloride

The investigational product, a targeted alpha-pharmaceutical (a radiopharmaceutical emitting alpha radiation), is a ready-to-use solution for intravenous injection containing the drug substance radium chloride. The active moiety is the alpha particle emitting nuclide Ra-223, present as a divalent cation ($^{223}\text{Ra}^{2+}$).

Dose

Doses are given as kiloBecquerel (kBq) per kilogram body weight, with the corresponding dose given in millicurie (mCi) per kilogram in parenthesis. The term “dose” is used to describe the quantity of radioactivity from Ra-223 dichloride administered.

1. Introduction

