The goal of this initial study is to determine the safety of escalating doses of monthly Ra-223 dichloride in osteosarcoma patients with osteoblastic bone-forming metastases until MTD or a dose 100 kBq/kg dose is reached (whichever is first). Radium-223 dichloride will be given monthly for up to 6 cycles and side effects of this bone-targeted therapy on monthly blood counts and alkaline phosphatase will be determined. After 3 and 6 doses patients will have imaging to compare ^{99m}TcMDP uptake to baseline and other imaging as clinically indicated including ¹⁸F-FDG PET-CT, Na¹⁸F and/ chest CT. Anatomic imaging (CT or MRI) of all sites of disease along with chest CT at baseline and restaging for all patients will be done to allow for assessment of RECIST progression. RECIST progression will determine progressive disease regardless of other imaging.

Table 1. Ra-223 dichloride Dose Escalation scheme (N=3/cohort)

Dose level:	kBq/kg	N
-1	25	--
0 (starting dose)	50	3
1	75	3
2	100	8
Expansion cohort	MTD	6

Anticipated Total N = 9- 20 (N= 20 assumes reaching 100 mBq/kg MTD)

***Imaging:** Three modalities will be compared
pre vs after dose 3 and after dose 6
ΔSUV of ¹⁸F PET-CT
ΔSUV Na¹⁸F PET-CT
Δ activity ^{99m}Tc-MDP SPECT -CT

Table 2. Decay and Marrow/Bone Ratios Clinically Useful Bone-seeking Isotopes

	Half-life	*Ratio of Surface	Particle	MeV particle	Range
	Days	Bone : red marrow		Emission energy	(mm)
¹⁵³ Sm-EDTMP	2	4.4	Beta	0.66 max 0.22 average	0.6
⁸⁹ SrCl ₂	50.5	1.6	Beta	0.58	2.4
²²³ RaCl	11.4	10.3	Alpha	27.4	<0.1

* Bone surface to red bone marrow radioactivity dose ratio

Table 3. Comparison of Alpha and Beta Particles from Bone-Seeking Cancer Drugs

Characteristic	Alpha	Beta
Range (um)	40-90	50-6000
Linear Energy Transfer*	60-230	0.015-0.4

Relative mass	7000**	1**
DNA hits to kill a cell	1-5	100-3000
Cytotoxic against G ₀ cells	Yes	No
Effective against “radio-resistant” cells	Yes	No

*(LET; keV/μm)

**Alpha particles are dense particles (i.e. like a helium nucleus); beta particles are electrons

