6.2.1 Radium-223 dichloride

6.2.2 Treatments to be administered

Ra-223 dichloride will be administered as a slow bolus IV injection at intervals of every 4 weeks for up to 6 cycles.

- Dose (50, 75, or 100 kBq/kg) will be assigned in cohorts of 3 after study registration in CORE.
- Dose #1 should be given within 30 days of study registration
- At least 3 patients will be required to successfully complete 6 weeks of therapy before advancing to the next cohort.
- Patients will receive the same Ra-223-dichloride dose as dose #1 for all subsequent doses.
- Monthly dosing (q 4 weeks +/- 6 days) as slow iv bolus for up to a total of 6 doses
- Monthly doses will be delayed, but no more than 2 weeks from scheduled dose for any grade 3 hematologic toxicity.

Criteria for subsequent doses (i.e. doses 2-6):

- Hematologic Toxicity (if present): Hb, ANC, and platelets- resolved to grade 2 or less within 6 weeks of prior dose. Since lymphopenia may be chronic, this will not be a criteria for subsequent doses
- All toxicities must be resolved to grade 2 or less in order to begin subsequent cycles
- Performance status ECOG 0 to 2
- Alkaline phosphatase stable or improving at the discretion of the treating physician
- Not on oxygen
- Not pregnant
- After dose #3 and before dose #4: stable disease or better in indicator lesions as determined by quantitative nuclear medicine imaging (^{18}F FDG PET-CT, quantitative $^{99\text{m}}\text{Tc}$ -MDP SPECT/CT, or Na^{18}F PET/CT) or RECIST criteria on anatomic imaging (note: often osteosarcoma "indeterminate" lesions 1-9 mm remain stable or have minimal change depending on chest CT technique).
- Anatomic imaging (CT or MRI) of all sites of disease along with chest CT at baseline and restaging for all patients will be done to allow for assessment of RECIST progression.
- RECIST progression will determine progressive disease regardless of other imaging.

For the Phase I aspect of the protocol, prior to advancing/changing dose levels, a cohort summary must be completed and submitted to the Clinical Research Monitor in the IND Office.

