beforehand and given suitable personal protection equipment (i.e. universal blood and body fluid precautions - especially when handling ashes containing potentially radioactive bone fragments. Calculations and the rationale for radiation dose estimates are available upon request (see investigators Brochure).

Definition of Dose-Limiting Toxicities (DLTs):

Toxicities will be graded in severity according to the guidelines outlined in the NCI Common Terminology Criteria for Adverse Events (CTCAE) version 4.0 (publish date 28-May-2009). Dose-limiting toxicities include all adverse experiences that are related to study medication, and clearly not related to disease progression or intercurrent illness.

Based on prior experience with other bone seeking radiopharmaceuticals and Ra-223 dichloride in prostate cancer patients, the expected dose limiting toxicity (DLT) will be hematologic. Lymphopenia is common in patients with bone metastases and will be monitored, but not considered a DLT in this protocol. Any grade 4 anemia, any grade 4 neutropenia for >7 days or grade 4 neutropenia with fever (a single temperature greater than 38.3°C or a sustained temperature of $\geq 38^\circ\text{C}$ for more than one hour) and grade 3 or 4 thrombocytopenia with clinically significant bleeding will be dose limiting. Grade 3 non-hematologic toxicities except for nausea, emesis or diarrhea that are controlled with maximal medical management within 72 hours will be considered dose-limiting. DLTs will only be monitored during the first 6 weeks of treatment. Ongoing toxicity that causes a delay of more than 2 weeks in starting the next cycle will also be dose-limiting if it occurs during the first cycle.

Dose Modification and Escalation

Every effort should be made to administer the full dosing regimen of Ra-223 dichloride. Adjustment of dose level is not permitted.

- A minimum of 3 patients initially will be enrolled at the first dose level.
- If at least 2 patients are observed to have a dose-limiting toxicity (DLT), the MTD will have been exceeded and no further patients will be enrolled at this dose level or at any higher dose level. The prior dose level is defined as the MTD (unless only 3 patients have been treated at that level, in which case it is the tentative MTD).
- If 0 of the 3 patients are observed to have DLT during the DLT assessment period, the dose level is escalated one step for the next cohort of 3 patients, and the process continues as above.

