- If exactly 1 of the 3 patients treated show DLT during the DLT assessment period, 3 additional patients are treated at the current dose level.
- If none of these additional 3 patients show DLT during the DLT assessment period, the dose level is escalated for the next cohort of 3 patients, and the process continues as above; otherwise, the prior dose level is defined as the MTD (unless only 3 patients have been treated at that level, in which case it is the tentative MTD).
- A tentative MTD becomes final when a total of 6 patients are treated with less than 2 showing DLT.
- If 2 of the first 3 patients have hematologic DLT, then next cohort will be dose level -1.

Study visits during the treatment period should occur at 4 weeks intervals (within a window of +/- 7 days). **Dosing delays** may be instituted under the following circumstances:

Disease progression:

The Investigator should delay cytotoxic chemotherapy, other systemic radioisotope, hemibody external radiotherapy or other investigational drug until the follow-up period. If such treatments have to be given during the treatment period, further study drug administrations must be discontinued. Patients with disease progression may continue other treatment at the Investigator's discretion.

Myelosuppression:

Treatment-related changes in hematology parameters may occur.

- Blood transfusion is acceptable between study drug administrations. Use of biologic response modifiers, such as G-CSF or GM-CSF, is allowed in the management of acute toxicity.
- If myeloid growth factors are required for the management of acute toxicity this event should be considered a DLT.

Gastrointestinal events:

Diarrhea should be treated as per local practice. A further dose of study medication should not be given before diarrhea is recovered to CTCAE v4.03 Grade 2 or baseline levels.

Nausea or vomiting should be treated as per local practice. A further dose of study medication should not be given before nausea or vomiting is recovered to CTCAE v.4.03 Grade 2 or baseline levels.

For any grade 3 hematologic toxicity for >14 days, study drug administrations must be discontinued (grade 4 events of anemia and neutropenia >7 days are dose-limiting).

Spinal Cord Compression:

If the patient experiences spinal cord compression during the treatment period, the patient should be treated for the event, and this will be considered disease progression.

Surgical Intervention:

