8.3 Statistical and analytical plans: as above

8.4 Planned interim analyses: yearly at time of IND review

8.5 Determination of sample size

Dose escalation phase: 3 dose levels using standard 3+3 design (N=9)

Cohort expansion N=6

9. Data handling and quality assurance

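### Section 8.5 gives 9 patients in escalation and the Synopsis gives 14; the 5-patient gap is the unexplained 8 at 100 kBq/kg in Table 1

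*Combined protocol and SAP*

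**What the plan says.** Three places give patient numbers.

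- **Synopsis, Number of subjects:** "Dose escalation N=14; dose expansion N=6 ;total= 20".
- **Section 4, Table 1:** the heading is "Ra-223 dichloride Dose Escalation scheme (N=3/cohort". The rows give 3 patients at 50, 3 at 75 and 8 at 100 kBq/kg, and 6 in the expansion cohort. Below the rows stands "Anticipated Total N = 9- 20 (N= 20 assumes reaching 100 mBq/kg MTD" (the unit is printed as mBq/kg, whereas the table's dose column is in kBq/kg).
- **Section 8.5, Determination of sample size:** "Dose escalation phase: 3 dose levels using standard 3+3 design (N=9", followed by an expansion of 6. The section prints no total and does not mention 8, 14 or 20.

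The enrolment rules are in the part headed Dose Modification and Escalation, after section 6.2.9. With no DLT in three patients, the next level opens with three. With exactly one DLT in three, "3 additional patients are treated at the current dose level". A tentative MTD is confirmed on six patients. Section 5.2.3 allows replacement of patients who leave for reasons unrelated to the study, but sets no number.

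**The concern.** The section that should justify the sample size does not support the number in the Synopsis. Its 9 is three levels of three, which is what results when no level needs a second group of three. It is not labelled as a minimum or as one path among several, although the escalation rules require more patients after one DLT in three. The Synopsis and Table 1 rest on a larger figure whose only distinctive ingredient, the 8 at the top dose, has no stated origin and does not fit the table's own heading.

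At stake is what enrolment is being approved, and on what basis. All of the discrepancy falls at the highest dose. If 100 kBq/kg is the MTD, Table 1 plans 8 + 6 = 14 patients there and section 8.5 implies 3 + 6 = 9. That matters for how much safety description to expect at that dose, since the primary objective includes a comparison of safety across 50, 75 and 100 kBq/kg.

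**Working it through.** **1. Reproduce the stated figures.**

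| Source | Escalation | Expansion | Total |
|---|---|---|---|
| Synopsis | 14 (printed) | 6 | 20 (printed) |
| Table 1 rows | 3 + 3 + 8 = 14 (by addition) | 6 | 14 + 6 = 20 (top of its printed range) |
| Section 8.5 | 3 × 3 = 9 (printed) | 6 | 9 + 6 = 15 (by addition, not printed) |

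The Synopsis and Table 1 agree with each other. Section 8.5 does not reproduce them.

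**2. Locate the gap.** Escalation: 14 − 9 = 5. Total: 20 − 15 = 5. The 50 and 75 kBq/kg rows hold 3 in either account, so the gap is the top row: 8 − 3 = 5.

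**3. What the written rules can produce.** Assume cohorts of exactly 3 and no replacements. No DLT rate needs to be assumed.

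- A level stops at 3 after 0, 2 or 3 DLTs in the first three. It goes to 6 after 1 in 3, or when a tentative MTD is confirmed. N at a level is therefore 3 or 6, never 8.
- Every escalation count is then a multiple of 3, and so is that count plus 6. Neither 14 nor 20 is a multiple of 3.
- If all three levels open, escalation takes 9, 12, 15 or 18. The minimum is 3 + 3 + 3 = 9 and the maximum is 6 + 6 + 6 = 18.
- Adding the expansion of 6 gives 15, 18, 21 or 24. The 15 takes three patients at each level as enough before expansion.

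**4. Compare with Table 1's range.** The anticipated total is 9–20. Both 9 and 15 lie inside it; the like-for-like figure is 15, because the range refers to totals. The rule-based maximum of 24 exceeds 20 by 4, before any replacement.

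**5. One candidate for the 8.** Six patients at 100 would give 3 + 3 + 6 + 6 = 18, and 20 − 18 = 2, so the 8 could be 6 plus 2 replacements. This is conjecture: section 5.2.3 gives no number, and nothing ties replacements to the 100 kBq/kg row.

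**The case against.** The strongest reply is that the final N of a 3+3 design depends on outcomes. Section 8.5 gives the base path and the Synopsis a larger planning figure. Table 1 calls its total anticipated, gives a range that contains both 9 and 15, and ties the 20 to reaching the top dose. Much of this stands, and it limits the point. A reader might infer that the protocol holds two rival enrolment plans, 15 and 20. The documents do not support that: 15 is printed nowhere, and the only stated totals, 20 and 9–20, are compatible. What the reply does not cure is that section 8.5 leaves its 9 unlabelled, that the Synopsis states 14 without qualification, and that nothing derives either from the other.

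A second reply is that cohort sizes are worded as floors: "At least 3 patients will be required to successfully complete 6 weeks of therapy before advancing to the next cohort" in section 6.2.2, and "A minimum of 3 patients initially will be enrolled at the first dose level" under the escalation rules. For that reason, and because replacements are allowed, it would go too far to say that 8 patients at a level cannot occur. But the second wording concerns the starting dose only. The first governs moving up to a further cohort, and none is planned above 100. Section 6.2.2 also assigns doses in threes. Neither wording yields 8.

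It may also be said that 24 is an extreme path and that a planning figure need not be the maximum. That is fair: 24 needs a second group of three at both lower levels and six at the top. It shows only that 20 is not an upper bound under the rules.

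**Conclusion.** The point holds. Escalation N is 9 in section 8.5 and 14 in the Synopsis and Table 1, a difference of 5 patients that lies entirely in the 100 kBq/kg row. The 8 in that row is unexplained, and 8, 14 and 20 do not follow from the stated rules on two assumptions: cohorts of exactly 3, and no replacements. On the same assumptions, 20 is not a maximum.

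The consequence is modest. A reader might infer that the trial's conclusions or its dose decisions are compromised; they are not. No hypothesis test, power or precision statement uses N, and escalation follows the DLT rules whichever figure is used. What is affected is the planned enrolment, its justification, and whether 20 means evaluable patients or everyone enrolled. I rate it minor to should-fix. The conflict is plain on the page, so confidence in it is high; the reason for the 8 remains unknown.

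**What to change.** - State the same escalation N and total N in the Synopsis, Table 1 and section 8.5.
- Give the basis in section 8.5 from the 3+3 rules: 9–18 evaluable patients in escalation if all three levels open, and 15–24 with the expansion of 6. If a single planning figure inside that range is used, say which path it assumes.
- Say whether the figure counts evaluable patients or all subjects including replacements.
- Explain the 8 at 100 kBq/kg or correct it, so that the row agrees with the table's heading.

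The cost is text edits in three places. The planned enrolment figure may need updating, possibly to somewhat above 20. The design, the doses and the DLT rules are unchanged.

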1.1 Background

Ra-223 dichloride is potentially a very low toxicity and high efficacy targeted agent for osteosarcoma, an osteoblastic bone-forming tumor. Because of low marrow toxicity of this radiopharmaceutical, knowledge of the MTD in this patient population is needed to develop future protocols. Use of Ra-223 dichloride in osteosarcoma should reduce the morbidity of therapy and mortality from metastases. The goal of this initial study is to determine the safety of escalating doses of monthly $^{223}\text{RaCl}_2$ in osteosarcoma patients with osteoblastic bone-forming metastases until MTD or a dose 100 kBq/kg dose is reached (whichever is first). Ra-223 dichloride will be given monthly and side effects of this bone-targeted therapy on monthly blood counts and alkaline phosphatase will be determined. After 3 and 6 doses patients will have imaging to compare $^{99\text{m}}\text{TcMDP}$ uptake to baseline and other imaging as clinically indicated including ^{18}F -FDG PET-CT, Na^{18}F and/ chest CT. Evaluations will include anatomic imaging (CT or MRI) of all sites of disease along with chest CT at baseline and restaging for all patients to allow for assessment of RECIST progression. RECIST progression will determine progressive disease regardless of other imaging. If well tolerated at the MTD, an additional 6 patients will be studied to better define toxicity and obtain data to support future investigation of Ra-223 dichloride with other agents and modalities (e.g. other drugs, surgery or external beam RT) for improved treatment of osteosarcoma.

